Monotherapy Anticoagulation To expedite Home treatment of venous thromboembolism (MATH VTE)

BMS PROTOCOL NUMBER: CV185-562

Sponsor: Indiana University

[name]
Vice Chair of Research
Department of Emergency Medicine
Professor, Department of Cellular and Integrative Physiology
Indiana University School of Medicine
[name]
[name]
[name] office
[name] cell
[contact]

Version 4.2

SYNOPSIS

Observational Study Protocol CV185-562

Protocol Title: Monotherapy Anticoagulation To expedite Home treatment of venous thromboembolism (MATH VTE)

Department: Emergency Medicine

Objective(s): Measure 30 day post diagnosis readmission rate of emergency department patients diagnosed with deep vein thrombosis or pulmonary embolism (venous thromboembolism, VTE) and treated at home with apixaban.

Study Design: Prospective registry

Study Population: Adults with new or recurrent VTE

Data Collection Methods: Patient reported by telephone and medical record review

Data Analyses: Point estimate with 95% confidence interval

Sample Size/Power: N=850 to narrow top limit of 95% CI for proportion of patients readmitted for bleeding or recurrent VTE within 30 days

TABLE OF CONTENTS

| | |
|---|----|
| TITLE PAGE | 1 |
| SYNOPSIS..... | 2 |
| TABLE OF CONTENTS..... | 3 |
| 1 INTRODUCTION | 5 |
| 1.1 Study Rationale..... | 5 |
| 1.2 Research Question | 6 |
| 2 OBJECTIVES..... | 6 |
| 2.1 Primary Objectives | 6 |
| 2.2 Secondary Objectives | 6 |
| 2.3 Exploratory Objectives | 7 |
| 3 STUDY DESIGN | 7 |
| 3.1 Overview of Study Design..... | 7 |
| 3.2 Study Population..... | 8 |
| 3.2.1 Inclusion Criteria | 8 |
| 3.2.2 Exclusion Criteria | 9 |
| 3.3 Data Source/Data Collection Process | 10 |
| 3.4 Definitions of Study Variables | 11 |
| 3.4.1 Outcomes/Endpoint Variables | 12 |
| 4 STATISTICAL ANALYSIS | 12 |
| 4.1 Statistical Analysis Methods..... | 12 |
| 4.1.1 Analysis Plan for Primary Objective | 12 |
| 4.1.2 Analysis Plan for Secondary Objectives | 13 |
| 4.1.3 Analysis Plan for Exploratory Objectives | 13 |
| 4.2 Power/Sample Size | 13 |
| 5 STUDY CONDUCT..... | 13 |
| 5.1 Ethics Committee Review and Informed Consent..... | 14 |
| 5.2 Responsibilities within the Study | 14 |
| 5.3 Confidentiality of Study Data..... | 14 |
| 5.4 Quality Control | 14 |
| 5.5 Database Retention and Archiving of Study Documents | 15 |
| 6 ADVERSE EVENT REPORTING | 15 |
| 6.1 Adverse Event Definitions..... | 15 |

1 INTRODUCTION

1.1 Study Rationale

This work seeks to generalize a protocol to improve the transition of care of patients with venous thromboembolism (VTE, including both deep vein thrombosis, DVT, and pulmonary embolism, PE) from the emergency department (ED) to home treatment. We hypothesize a <2% rate of 30 day re-hospitalization for recurrent VTE or bleeding in patients selected as low risk by the modified Hestia criteria or physician discretion and sPESI negative. The 2% upper limit of the 95% CI threshold is justified based upon data from AMPLIFY and pooled data from EINSTEIN DVT and PE which show a point estimate 30 day VTE recurrence rate of 1-1.2%.^{1,2} For patients deemed low risk in the present study, it can reasonably be predicted this rate will be considerably lower. The 30 day incidence of major bleeding were <1.0% in both AMPLIFY and EINSTEIN, and for patients with low risk of bleeding, the rate can be expected to be about 0.5% with upper limit 95% CI <1.0%.³ Additionally, the 90 day incidence of the composite rate for VTE recurrence and major bleeding reported in systematic reviews and meta analyses of outcomes of low risk VTE patients diagnosed in the ED and treated at home with vitamin K antagonists (VKAs) was 18/785 (2.2%, 95% CI 1.4-3.6%).^{4,5} Den exer et al randomized 275 Hestia negative patients to be treated with VKAs at home; 90 day follow up found 3 with recurrent VTE and 3 with major bleeding (6/275, 2.2%).⁶ Taken together, we submit these data which support the assertion of the upper limit 30 day failure rate (composite of VTE recurrence and bleeding) <2.0% to constitute a reasonable and prudent expectation of standard care. Recent evidence indicates the safety and acceptance of home treatment of both DVT and PE.^{7,8} Patient interviews indicate a strong patient preference to this approach over use of injectable low molecular weight heparin and vitamin K antagonists (e.g., <https://iu.box.com/riva-patient-interviews>). However, clinicians remain reluctant to discharge DVT and PE patients because lack of a “hard wired” system to guarantee patient follow-up⁹. **To help facilitate this transition in care**, in 2013 in Indianapolis, the project leader/principal investigator, implemented an outpatient treatment protocol using target specific anticoagulants (TSA) for patients with VTE in two hospitals with a low risk of treatment failure and drug related side effects. Most importantly, this included two dedicated clinics (known locally as the KLOT clinics) for these patients to follow-up. Two manuscripts describing the outcomes of the first 106 subjects, as well as a case-control cost effectiveness study have been published.^{10,11} A third paper documented good patient outcomes and quality of life equal to patients treated with usual care.⁹ With more experience, we have found the transition of care can occur from the ED to primary care physicians and even to existing anticoagulation clinics.

Clinicians encounter one low-risk VTE patient who could safely be treated at home in about every 600 patient encounters.¹²⁻¹⁵ Systematic reviews and meta-analyses of literature have suggested a <1% failure rate and <1% 30 day bleed rate associated with home treatment of patients with low-risk PE as determined by validated prognostic scores. However, even after careful selection of VTE patients using existing rules, patients have a small probability of an adverse outcome in the short term, helping to fuel clinician desire for a system of patient follow-up.^{16,17} The predicate work used the Hestia criteria for both DVT and PE with awareness that Hestia was designed and initially validated for PE patients. Rationale for using Hestia in DVT patients is based upon our survey and in observation of practice; emergency physicians will not discharge DVT patients who fail any of the Hestia criteria. Moreover, in theory because many DVT patients have PE that may be asymptomatic and in absence of pulmonary vascular imaging, clinicians cannot determine which DVT patients have silent PE, the safest option is to screen them as if they have PE¹⁸.

This is a study of implementation and dissemination, conducted with a framework to enhance its value and subsequent adoption.¹⁹ The primary deliverable of this study will be 1. A detailed written protocol, with annotations and unique commentary (i.e. “pearls”) by physicians and advanced practitioners who implemented the protocol 2. The outcomes of 850 patients demonstrating the rate of return to the hospital at 30 days. The rationale for 30 days is that in surveys of risk tolerance, 30 days is the most common time duration identified by most emergency physicians as their “responsible” period for the patient.^{9,20}

Innovation

This work expands a novel and patient-centered clinical protocol to at least five other states, at least six other independent hospitals, engages primary care physicians, repurposes and integrates existing anticoagulation clinics and provides education and know-how to use urgent care/fast track clinics for follow-up.

This innovative approach will allow generalization of this protocol across the US. Additionally, primary care physicians will be involved and offered education/experience to increase their involvement and acceptance of these patients in follow-up.

For physicians, this work will show a pathway to liberating low-risk patients with VTE from the need for hospitalization. From prior work, these patients make remarkable statements of gratitude, which we believe will translate into high patient satisfaction scores and likelihood to recommend the hospital system to their friends.

1.2 Research Question

Can emergency department patients with acute pulmonary embolism and/or deep vein thrombosis, identified as low risk by objective criteria, be treated at home with monotherapy anticoagulation with an <2% rate of bleeding requiring re-hospitalization or objectively confirmed recurrent VTE requiring re-hospitalization within 30 days.

2 OBJECTIVES

2.1 Primary Objectives

Evaluate the primary effectiveness of an implementation protocol to identify and manage care of patients diagnosed with DVT and/or PE who are discharged from the ED and treated with apixaban. Treatment failure rate, defined as the numerator, comprising the sum of subjects treated in this protocol who are re-hospitalized for >24 hours within 30 days of enrollment for either objectively diagnosed VTE or for major or clinical relevant non-major bleeding related event, divided by the denominator of enrolled subjects. Protocol success will be defined by the upper limit 95% CI for this proportion < 2.0%.

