3.2.1 Inclusion Criteria

Criteria for initial VTE diagnosis require a filling defect interpreted as positive on computerized tomographic pulmonary angiography, a ventilation-perfusion lung scan interpreted as high probability, or an incompressible vein observed on venous ultrasound of an extremity or jugular vein. Screening includes electronic surveillance of the “VTE home treatment order set” which ensures low risk criteria and then provides appropriate medication, including apixaban as an option, and discharge instructions. Enrollment occurs at the time of written informed consent.

1. Patients must be **low risk**, as defined by either A or B below:

A. The modified Hestia criteria:

- Systolic blood pressure > 100 mm Hg
- No thrombolysis needed
- No active bleeding
- SaO₂ >94% while breathing room air
- Not already anticoagulated
- No more than two doses of IV narcotics in the emergency department
- Other medical or social reasons to admit
- Creatinine clearance >30mL/min
- Not pregnant, severe liver disease or heparin induced thrombocytopenia

OR

B. The physician opinion that a patients' overall social and medical situation is favorable for home treatment and the patient has a zero score on the simplified pulmonary embolism severity index (sPESI).

All of the following must true:

- Age < 81 years
- No history of cancer
- No history of heart failure or chronic lung disease
- Pulse < 110 beats/min
- SBP > 99 mm Hg
- O₂ sat >89%

We have chosen either criteria because both have been found equal in terms of safety for outpatient treatment of PE.^{6,22} Hestia includes implicit questions that most emergency physicians would use as criteria for discharge (e.g., overall medical status and social situation), whereas sPESI does not. For that reason, we have added the additional gestalt assessment question about physician discretion.

[figure not shown]
2. Patients must be discharged in <24 hours after triage in an ED visit with diagnosis of VTE using objective criteria in the emergency department.

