3.3 Data Source/Data Collection Process

The figure below demonstrates the data flow process. Each site will complete an electronic case report form that will be linked by a study ID (e.g. CMC001) to the study site enrollment registry, maintained at the study site. The study deliverable is a PHI deidentified REDCap data set (appendix). Placards will be posted in the emergency department with a flow diagram similar to the one diagrammed above. Each site will create a specific “VTE home treatment” order set which prints prescriptions. Subjects will follow-up in designated anticoagulation centers or with a primary care physician. The duration of anticoagulation will usually be at least 3 months.(16) Patients will be identified by query of the electronic order set. Outcomes will be assessed by medical record review and/or a telephone call to each patient made after 30 days after discharge from the emergency department to document outcomes from the time of discharge to 30 days thereafter.

The primary efficacy and safety aims will be assessed by telephone survey and medical record review at or after 30 days, asking the subject explicitly about any change in health status, any unscheduled visit to an emergency department or other healthcare provider, re-hospitalizations, VTE diagnoses, or bleeding events. The script and procedures for the phone call, including handling disconnected numbers, and non-answers will be in the guidance document.

Definitions of recurrent VTE: Study personnel will perform a chart review to confirm suspected recurrent PE/DVT, which will require explicit radiographic or ultrasonic evidence of PE/DVT.

The definition of **re-hospitalization for bleeding** requires chart review demonstrating explicit written decision-making by the admitting emergency physician that a patient was admitted (requiring >24 hour stay) for medical or procedural care to manage objective or suspected bleeding. This would include charted evidence of initially suspected but later disproven bleeding such as gastrointestinal bleeding. Bleeding events will be further characterized as **major bleeding or clinically relevant non-major bleeding**, using published criteria, further defined in the guidance document and using previously established criteria.^{3,21}

Secondary objectives

Discontinuation of apixaban. During the follow-up telephone call, patients will be asked if they discontinued apixaban and if so, what anticoagulant they are currently taking.

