3.4.1 Outcomes/Endpoint Variables

The primary outcome measures the frequency of one or more episodes of a subject returning for medical care resulting in hospital stay > 24 hours as a direct result of either recurrent VTE or major or clinical relevant non-major bleeding within 30 days of VTE diagnosis that initiated enrollment. For the purpose of this protocol, these events are synonymous with the term treatment failure endpoints. Each case requires medical documentation indicating the reason for hospitalization was for treatment, diagnosis or monitoring of the recurrent VTE or bleeding condition. For example, if a subject returns to an emergency department for chest pain, and reports a nosebleed on the same day, and is hospitalized for testing related to the chest pain, and is not found to have recurrent VTE, the subject does not meet a primary failure endpoint. However, if the subject were admitted for nose packing, or was discovered to have a new PE, then in either case, the subject would meet the primary failure endpoint.

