5.1 Ethics Committee Review and Informed Consent

The protocol will be implemented as standard of care. Data will be obtained as part of a quality assurance registry, which will be reviewed by each institutional review board for requirements regarding verbal or written informed consent or exemption from IRB review.

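### The primary endpoint's 30-day window has three conflicting starting points (written consent, VTE diagnosis, ED discharge), and one failure more or less can decide success

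*Protocol*

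**What the plan says.** The protocol gives the same 30-day primary endpoint three origins.

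- **Enrollment.** Section 2.1 counts subjects "re-hospitalized for >24 hours within 30 days of enrollment", and 4.1.1 repeats this for the primary analysis. Section 3.2.1 fixes the moment: "Enrollment occurs at the time of written informed consent". The adverse-event period in section 6 is also 30 days from enrollment.
- **VTE diagnosis.** Section 3.4.1, which defines the primary outcome, counts events "within 30 days of VTE diagnosis that initiated enrollment". The synopsis agrees: "Measure 30 day post diagnosis readmission rate".
- **ED discharge.** Section 3.3 says the record review or telephone call is "to document outcomes from the time of discharge to 30 days thereafter".

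Two further statements bear on when enrollment happens. Section 3.3 says "Patients will be identified by query of the electronic order set", and 3.2.1 describes screening as electronic surveillance of that order set, which also supplies the medication and discharge instructions. Section 5.1 leaves each institutional review board to decide on "requirements regarding verbal or written informed consent or exemption from IRB review". No section sets a latest time for consent relative to discharge.

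The denominator is enrolled subjects (2.1, 4.1.1). Success means an exact binomial upper 95% limit below 2.0%, with 850 subjects planned.

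**The concern.** This endpoint carries the trial's only pass/fail rule, so it must be clear which events count. As written, the same re-hospitalization can be a failure under one section and not under another.

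The choice of origin may also not be neutral. Patients are found through an order set used at discharge, and the protocol does not say that consent must already have been obtained. For a patient who consents after going home, a clock started at consent excludes any failure between discharge and consent. A patient who is re-hospitalized before being approached may never consent, and so may never enter the numerator or the denominator. The first is left truncation and the second is selection. Both would push the observed failure rate down, toward a declaration of success.

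Separately, a site working with verbal consent or an exemption has no written consent. Read literally, its patients have no enrollment time and so no start to the window in 2.1.

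**Working it through.** **Step 1. Set the windows side by side.** Let discharge from the index visit be day 0 and written consent be day c.

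| Source | Window |
|---|---|
| 2.1, 4.1.1 (with 3.2.1) | day c to day c + 30 |
| 3.4.1, synopsis | diagnosis, shortly before day 0, to 30 days later |
| 3.3 (data collection) | day 0 to day 30 |

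**Step 2. Consent in the ED before discharge.** Section 3.2.1 requires discharge less than 24 hours after triage in the visit at which VTE is diagnosed. Diagnosis, consent and discharge then all fall in that interval, so the origins differ by less than a day. No re-hospitalization can precede consent. The conflict affects only events at the very end of the window.

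**Step 3. Consent after discharge (c > 0).**
- An event between day 0 and day c is collected under 3.3 and counts under 3.4.1, but not under 2.1 and 4.1.1.
- An event between day 30 and day c + 30 counts under 2.1 and 4.1.1, but lies outside the collection period in 3.3 and outside the 3.4.1 window.
- A patient who fails before day c and is never enrolled is missing under every definition.

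**Step 4. No written consent (verbal or exempt site).** Here c is undefined, and so is the 2.1 window.

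**Step 5. How many events does it take to matter?** Inputs: N = 850 (synopsis, 4.2), the exact binomial limit (4.1.1) and a threshold of 2.0% (2.1). With x failures, the two-sided 95% exact upper limit is the 0.975 quantile of a Beta(x + 1, 850 − x) distribution.

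| Failures | Printed in 4.2 (%) | Exact upper limit (%) | Below 2.0%? |
|---|---|---|---|
| 6 | 1.5 | 1.530 | yes |
| 8 | 1.8 | 1.846 | yes |
| 9 | 1.9 | 2.0004 | no |
| 10 | 2.0 | 2.153 | no |

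The planning scenario of 3 recurrences plus 3 major bleeds gives 6 failures, and its printed limit of 1.5 is reproduced. The rows for 9 and 10 are not; that is a separate matter. It does not change the point here. On the printed table, 9 failures (1.9) would pass and 10 (2.0) would not be below 2.0, so one failure still separates success from non-success.

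Suppose 9 subjects truly fail and 1 of them fails before consent. If that event is left out but the subject stays in the denominator, the limit for 8/850 is 1.846%. If the subject is never enrolled and not replaced, the limit for 8/849 is 1.848%. Either way, a result that should fail (2.0004%) passes.

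**Step 6. What cannot be computed.** The documents give neither the share of subjects who would consent after discharge, nor the delay, nor the timing of failures within the 30 days. The size of any bias is therefore not determined.

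**The case against.** The strongest reply is that no section says consent follows discharge. Querying an order set is a way of finding patients and does not fix when consent is taken. Section 3.4.1 speaks of the diagnosis as what initiated enrollment, and section 6 ties its 30-day period to the order set; both suggest that enrollment belongs to the index visit. If so, Step 2 applies and the practical difference is about a day. This stands as a limit on the concern: the bias is conditional and has not been shown. It does not remove the contradiction, because later consent is not excluded.

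It can also be said that early events in enrolled subjects are not lost as data, since 3.3 collects from discharge and 3.4.1 would count them. That is right. For enrolled subjects the question is which wording governs. Nor does any section bar a re-hospitalized patient from consenting, so non-enrollment of early failures is a possibility, not a certainty.

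A reader might go further and infer a calculable rise in the chance of wrongly declaring success, by shortening each subject's window in proportion to the consent delay. The documents do not support this. It needs an assumed delay applied to all 850 subjects, and it splices two competing definitions: a start at consent and an end 30 days after discharge. A window run wholly from enrollment is still 30 days long, so later events could partly offset earlier ones. Moreover, success at a true rate below 2%, such as 1.5%, is not a false conclusion.

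A reader might also call this immortal time. For a clock started at consent that is the wrong term; the possible defects are left truncation and selection.

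**Conclusion.** The protocol contradicts itself on the start of the primary endpoint's window: written consent in 2.1 and 4.1.1 (through 3.2.1), VTE diagnosis in the synopsis and 3.4.1, and ED discharge in 3.3. No section ranks them. The definition of enrollment in 3.2.1 also does not fit the consent options in 5.1. This rests on the text alone. It is a conflicting rule for the decision endpoint, not a detail that could be left to a separate analysis plan.

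The consequence depends on when consent is obtained. With consent in the ED, the origins differ by about a day at most. With consent after discharge, the enrollment clock would omit early failures and could leave some patients out altogether, and both lower the observed rate. The amount is unknown. It matters because the margin is a single event: 8 failures in 850 pass at 1.846%, and 9 fail at 2.0004%.

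**What to change.** 1. State one time zero, ED discharge of the index visit, in the synopsis and in 2.1, 3.3, 3.4.1, 4.1.1 and 6.
2. Count every failure of an enrolled subject from discharge to day 30, whatever the date of consent.
3. Rewrite the definition of enrollment in 3.2.1 so that it covers written consent, verbal consent and exemption as 5.1 allows.
4. Report the number of subjects who consented after discharge.

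Items 1 to 3 cost protocol wording only: 3.3 already collects from discharge, and neither the sample size nor the analysis method changes. Item 4 needs the consent and discharge times of each subject.

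Rewording cannot recover patients who fail before consent and are never enrolled; item 4 shows the reader how much room there is for that. Requiring consent before discharge, or enrolling consecutive patients at exempt sites, would address it more directly. But those steps change site operations and review-board arrangements, and they are not needed to resolve the contradiction.

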2.2 Secondary Objectives

- Frequency of subject-reported non-major bleeding within 30 days
- Frequency of discontinuation of apixaban in the first month as reported by subject or medical record.
- Total number of days of hospital stay in first 30 days
- Proportion of all subjects with VTE diagnosed in the emergency department treated with protocol

[figure not shown]
